5.1 PRIMARY ENDPOINT

The primary endpoints for the two trial parts, phase I and phase IIa are the:

- Rate of Adverse Events after study drug inhalation
- Rate of Adverse Events after combined inhalation and intravenous infusion of the study drug

This actually translates into the

- Proportion of patients with any adverse event occurring within 7 days of study drug inhalation
- Proportion of patients with any adverse event occurring within 7 days of study drug after combined inhalation and intravenous infusion of the study drug

As this study is exploratory and hypothesis generating in nature, no formal statistical testing will be implemented. The safety analysis will be descriptive and reported in total, by seriousness, relatedness, and severity. In addition, the safety events will be listed by participant. Handling of missing data points is described in [Section 6.6.1](#).

5.2 SECONDARY ENDPOINTS

5.2.1 Key secondary endpoints

This section is not applicable as no key secondary endpoint has been specified in the CTP.

5.2.2 Secondary endpoints

5.2.2.1 AUC_{0-672h} (the area under the concentration-time curve of DZIF-10c in serum over the time interval from 0 to 672 hours (i.e. post drug administration until Day 29))

Serum levels of DZIF-10c will be determined using a validated immunoassay. Non-compartmental analysis methods will be used to calculate pharmacokinetic parameters.

5.2.2.2 The frequency and magnitude of anti-drug antibodies targeting DZIF-10c

The following parameters will be assessed:

- The number and percentage of subjects with anti-drug antibodies (ADA) on Day 1, 15, 29, 57 and 91 by cohort and overall
- For subjects with ADA: the ADA titer on Day 1, 15, 29, 57 and 91

5.2.2.3 SARS-CoV-2 RNA shedding in nasopharyngeal swabs determined by qRT-PCR in SARS-CoV-2-infected individuals

Viral shedding is quantified as viral load (VL) in nasopharyngeal swabs by using a SARS-CoV2-RNA qPCR assay, and reported as PCR threshold cycle (CT) values. The transformation of CT into units of copies/mL is performed by using assay reference standards.

5.3 FURTHER ENDPOINTS

5.3.1 Successful virus isolation from nasopharyngeal swabs in SARS-CoV-2-infected individuals

Observance of a cytopathic effect (CPE) after inoculation of VeroE6 cells with virus transport medium and/or a decrease of the SARS-CoV-2-RNA-PCR CT value of cell culture supernatant by 3 or more within seven days of culture will be defined as successful virus isolation (i.e., presence of infectious virus in the respective sample).

5.3.2 SARS-CoV-2 RNA shedding in oropharyngeal swabs determined by qRT-PCR in SARS-CoV-2-infected individuals

Viral shedding is quantified as VL in oropharyngeal swabs by using a SARS-CoV2-RNA qPCR assay, and reported as PCR CT values. The transformation of CT into units of copies/mL is performed by using assay reference standards.

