Study Product and Placebo	
DZIF-10c is a recombinantly produced fully human monoclonal antibody of the IgG1k isotype that targets the spike protein (S) of SARS-CoV-2. When tested in vitro, DZIF-10c potently neutralizes SARS-CoV-2 and prevents viral infection.
 
Solvent for dilution (formulation buffer) of DZIF-10c will be used as placebo for inhalation. Sterile normal saline (0.9% NaCl) will be used as placebo for the intravenous administration.
 
Dose  A volume of 5 mL containing metered doses of 50 mg, 100 mg, or 250 mg of DZIF-10c (or placebo) will be inhaled. For the intravenous infusion of DZIF-10c, the targeted dose of 40 mg/kg requires SMC confirmation and may be reduced if a separate trial on the intravenous infusion of DZIF-10c (Uni-Koeln-4288, EudraCT: 2020-003503-34) defined a lower maximum tolerated dose.
 
Route of Administration  For the inhalation, DZIF-10c or placebo will be administered through a mouthpiece following aerosol generation using a mesh nebulizer. For the infusion, DZIF-10c or placebo will be administered by intravenous infusion after dilution in formulation buffer as necessary using a 0.2 <math>\mu</math>m in-line filter.

Treatment Duration	
DZIF-10c will be administered by a single inhalation or by a single inhalation followed by a single intravenous infusion.
 
Participants will be followed for 90 days after the administration of DZIF-10c or placebo.

Tentative Time Plan	First patient first visit (FPFV): Q4/2020 Last patient first visit (LPFV): Q2/2021 Last patient last visit (LPLV): Q3/2021 End of trial: Q3/2021 Final study report: Q2/2022

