### 1.5. DZIF-10c

DZIF-10c is a potent human SARS-CoV-2-neutralizing antibody that was identified from a blood sample of a COVID-19-convalescent patient obtained 35 days after diagnosis of infection. To isolate SARS-CoV-2-neutralizing antibodies from this and 11 additional patients, single memory B cells reactive to the SARS-CoV-2 spike protein were sorted using flow cytometry. Antibody heavy and light chain sequences were subsequently amplified from individually lysed cells using specific reverse transcription polymerase chain reaction (RT-PCR) and sequenced, facilitating the recombinant production of exact antibody replicates. Using this approach, the human monoclonal antibody HbnC3t1p1\_F4 was identified and later modified by eliminating the heavy chain C-terminal lysine to reduce potential charge heterogeneity, resulting in antibody DZIF-10c. DZIF-10c is a monoclonal antibody of the IgG1 kappa isotype with low somatic hypermutation compared to its germline sequence (% germline nucleotide identity of 93.2% and 96.1% for the heavy chain and light chain variable genes, respectively).

DZIF-10c targets the receptor binding domain (RBD) of the SARS-CoV-2 spike protein with high affinity. When tested *in vitro*, DZIF-10c demonstrates potent neutralizing activity both against authentic SARS-CoV-2 as well as SARS-CoV-2 spike-typed pseudoviruses. For example, infection of Vero E6 cells with the SARS-CoV-2 variant BavPat1/2020 was completely blocked in the presence of DZIF-10c at concentrations as low as 0.05 µg/ml as indicated by the absence of detectable cytopathic effects. Moreover, DZIF-10c demonstrated high activity against a panel of six SARS-CoV-2 pseudovirus variants with an average 50% inhibitory concentration (IC50) of 0.007 µg/ml in a neutralization assay using ACE2-expressing human 293T cells.

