### Assessment of the presence of infectious SARS-CoV-2

Viral transport medium will be incubated on VeroE6 cells to determine the presence of infectious virions. Cell culture supernatants will be assessed for virus production by qRT-PCR and/or cells will be visually inspected for the development of cytopathic effects. These assays will be performed at the Institutes of Virology at the University Hospital Cologne and/or the University of Marburg.

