## **5.9. Treatment**

### **5.9.1. Administration**

#### Inhalation

DZIF-10c or placebo will be administered as a single inhalation through a mouthpiece (Aerogen Ultra) using a mesh nebulizer (Aerogen Solo) to generate an aerosol. The inhalation procedure will require approximately 15-20 minutes.

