5.3.3 Successful virus isolation from oropharyngeal swabs in SARS-CoV-2-infected individuals

Observance of a CPE after inoculation of VeroE6 cells with virus transport medium and/or a decrease of the SARS-CoV-2-RNA-PCR CT value of cell culture supernatant by 3 or more within seven days of culture will be defined as successful virus isolation (i.e., presence of infectious virus in the respective sample).

5.3.4 Frequency of COVID19-related hospitalization and medically-attended health care contacts in SARS-CoV-2-infected individuals not previously hospitalized

For SARS-CoV-2-infected individuals, information is collected on hospitalization or medically-attended health care contacts (e.g., emergency room visit) and the relationship or association with SARS-CoV-2-infection is evaluated by the investigator.

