7.6.2.1 Successful virus isolation from nasopharyngeal swabs in SARS-CoV-2-infected individuals

Information will be shown for each assessment time point on whether live virus could be isolated in participating subjects or not. In addition, the relative frequency of positive samples will be shown per timepoint.

This endpoint will be evaluated on subjects from the subject set TS.

7.6.2.2 SARS-CoV-2 RNA shedding in oropharyngeal swabs determined by qRT-PCR in SARS-CoV-2-infected individuals

The same evaluations as proposed to be done for the secondary endpoint of SARS-CoV-2 RNA shedding in nasopharyngeal swabs determined by qRT-PCR in SARS-CoV-2-infected individuals shown in [Section 7.5.2.2.3](#) will be implemented for this endpoint. These evaluations will be based on all subjects in the subject set TS who have at least a baseline value and a second measurement in the respective time period of viral RNA shedding in OP swabs by qRT-PCR.

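### Drug carried over in swab medium may suppress virus culture in the DZIF-10c arms, so a lower culture-positive rate than placebo is not by itself evidence of less infectious virus shed

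*SAP*

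**What the plan says.** Protocol 5.2.3 describes the test for infectious virus: "Viral transport medium will be incubated on VeroE6 cells to determine the presence of infectious virions". SAP 5.3.1 (nasopharyngeal) and 5.3.3 (oropharyngeal) require a cytopathic effect, and/or a supernatant Ct fall of at least 3 within seven days; either finding "will be defined as successful virus isolation (i.e., presence of infectious virus in the respective sample". Only a positive is defined. For Group 2D, SAP 7.6.2.1 and 7.6.2.3 report isolation yes or no at each visit, and "the relative frequency of positive samples will be shown per timepoint", by arm. SAP 7.6.1.1 and 7.6.1.3 do the same by cohort in phase I. The objective served (Protocol 2.4) is the effect of DZIF-10c on shedding of infectious virions.

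On the drug, Protocol 1.5 reports that infection of Vero E6 cells by one virus variant "was completely blocked in the presence of DZIF-10c at concentrations as low as 0.05 µg/ml". On dosing, the Protocol Synopsis states: "A volume of 5 mL containing metered doses of 50 mg, 100 mg, or 250 mg of DZIF-10c (or placebo) will be inhaled". Protocol 5.9.1 gives the inhalation through a mouthpiece. In Group 2D (Protocol 4.1) two of the three arms inhale DZIF-10c at a target of 250 mg, one of these also receives it by infusion at a target of 40 mg/kg, and the control arm receives placebo by both routes.

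Under Protocol Appendix II B both swab types are taken before dosing and then on days 1, 3, 5 (optional), 7 and later. The SAP numbers each day one higher; the protocol's labels are used here.

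**The concern.** Both criteria for a positive culture need virus to infect cells and multiply in the dish. If the medium placed on the cells contains DZIF-10c, that growth can be held back whatever the participant was shedding. Placebo samples contain no such inhibitor, so any bias runs one way, toward DZIF-10c, and more participants would not remove it. In phase I, where all infected participants receive the drug, the same problem affects the fall from the pre-dose swab.

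Some negatives in the active arms may be a true effect, because virus can be neutralised in the airway before it is sampled. The assay as defined cannot separate that from neutralisation in the tube or the well. What is at stake is whether a difference in culture positivity between arms can be reported as a reduction in infectious shedding.

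**Working it through.** **Inputs from the documents.** Full block of Vero E6 infection at 0.05 µg/ml (Protocol 1.5; one variant, inoculum size not given). Inhaled dose 50, 100 or 250 mg in 5 mL (Synopsis). Epithelial lining fluid 20–40 mL, with deposition called limited but not quantified (Protocol 5.9.5).

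**Not in the documents, so assumed.** Deposited share, dilution of swab fluid into the medium and well, and airway half-life. The 20–40 mL is a lung-fluid volume. No upper-airway volume is given, so using it for throat or nasal fluid is itself an assumption.

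**The protocol's own statement first.** Protocol 5.9.5 expects 50 mg to give a lining-fluid level below total IgG (1–2 mg/mL). 50 mg / 20–40 mL = 1.25–2.5 mg/mL at full deposition. This falls below 1 mg/mL if deposition is under 40% (20 mL) or under 80% (40 mL), which is consistent with limited deposition.

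**Headroom.** 250 mg / 5 mL = 50 mg/mL = 50,000 µg/ml, and 50,000 / 0.05 = 1,000,000 times the blocking level. The 50 mg dose gives 200,000 times.

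**Level needed on the swab.** For the medium to reach 0.05 µg/ml after dilution of 1:10, 1:100 or 1:1000, the swab fluid must hold 0.5, 5 or 50 µg/ml. That is 0.001%, 0.01% or 0.1% of the nebulised concentration.

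**Range over time.** Ratio = (250,000 µg × share / volume) × 2^(−time/half-life) / dilution / 0.05. The grid has 96 combinations: share 0.1, 1, 10, 30%; volume 20, 40 mL; dilution 10, 100, 1000; half-life 4, 12, 24, 48 h.

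| Day | Lowest ratio | Highest ratio | Combinations above 1 |
|---|---|---|---|
| 1 | 0.002 | 5,300 | 72% |
| 3 | below 0.001 | 2,650 | 49% |
| 7 | about 0 | 660 | 27% |
| 14 | about 0 | 59 | 8% |

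These shares describe the grid and are not probabilities.

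**A middle case.** Share 10%, 30 mL, 1:100: 250,000 × 0.1 / 30 = 833 µg/ml; / 100 = 8.33 µg/ml; / 0.05 = 167 before clearance. With half-lives of 4 to 48 h the ratio is 2.6 to 118 on day 1, 0.0006 to 59 on day 3, and about 0 to 15 on day 7.

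**A narrower set.** Share 5–30%, dilution 1:30 to 1:100, a further 1- to 10-fold in the well. Low end: 250,000 × 0.05 / 40 / 100 / 10 = 0.31 µg/ml. High end: 250,000 × 0.30 / 20 / 30 = 125 µg/ml. Soon after dosing this is 6 to 2,500 times the blocking level, or 2.6 to 11.3 halvings. At an assumed half-life of 12–24 h, the low end lasts 2.6 × 12 h to 2.6 × 24 h = 1.3–2.6 days, short of the nominal day 3 swab. The high end lasts 5.6–11.3 days.

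**Infusion as a second source.** Assume 70 kg, a distribution volume of 3–6 L and mucosal fluid at 0.1–1% of serum. 40 × 70 = 2,800 mg; / 3–6 L = 467–933 µg/ml; × 0.001–0.01, then / 30–100, gives about 0.005–0.3 µg/ml in the medium, on either side of 0.05.

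**The case against.** The SAP never says that a negative culture means no infectious virus. Its gloss explains a positive, and the outputs are isolation yes or no and the share of positives. The converse is implied only by the objective in Protocol 2.4. That is correct, and it is why the point concerns how a between-arm difference is read.

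The documents give no deposition, clearance or dilution figure for the throat or nose, and the blocking concentration is for one variant. The drug enters by mouthpiece, so the nasopharynx is reached less directly. Handling follows a Lab Manual that was not supplied (Protocol 5.2.9), and a wash, dilution or other control there cannot be excluded. All of this stands. It limits the size but does not remove the mechanism.

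The endpoint is exploratory and descriptive. The main efficacy analysis is of viral RNA (Protocol 8.1.4, SAP 7.5.2.2.3), and subgenomic RNA is already planned (SAP 5.3.8). This also stands. It lowers the stakes and makes the remedy cheap.

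A reader might infer that the medium is far above the blocking level and that the endpoint must therefore favour DZIF-10c. The documents do not support that. On stated assumptions the day 1 level runs from below the threshold to thousands of times above it, and by day 7 most of the grid lies below.

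**Conclusion.** The concern holds in a limited form. Swab medium from DZIF-10c arms may carry enough drug to suppress growth on VeroE6 cells, mainly on days 1 and 3 and mainly in oropharyngeal swabs. A lower culture-positive rate than placebo therefore cannot, under SAP 5.3.1 and 5.3.3 alone, be read as less infectious virus shed. The possible bias has a known direction but an unknown size, because deposition, dilution and airway clearance are all assumed and a lung-fluid volume stands in for the sampled sites. The conclusion also assumes that the Lab Manual holds no carry-over control. The primary and secondary endpoints are unaffected.

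**What to change.** In SAP 5.3.1, 5.3.3, 7.6.1.1, 7.6.1.3, 7.6.2.1 and 7.6.2.3:

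- Label a negative result 'virus not cultured'.
- For every arm and cohort alike, tabulate per visit and swab type: culture positive; RNA positive but not cultured; RNA negative.
- State that between-arm differences in culture positivity at early visits may reflect drug carried into the culture and are not by themselves evidence of reduced infectious shedding, unless a carry-over control in the Lab Manual is cited.
- Show the subgenomic RNA result for the same swab where available, and base between-arm statements about replication on it. That readout does not depend on infection in the dish. SAP 5.3.8 leaves open which swab types are tested and places the results in a separate report, so the pairing has to be requested.

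Two tempting alternatives are not advised. Calling RNA-positive, culture-negative samples indeterminate only in the DZIF-10c arms would classify the same result differently by arm and set aside true neutralisation in the airway. Gating on a drug level in leftover medium would rely on an immunoassay described only for serum (Protocol 5.2.2, SAP 5.2.2.1).

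The cost is SAP wording and one cross-tabulation of data already collected. The downside is a weaker claim from the culture endpoint.

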5.3.3 Successful virus isolation from oropharyngeal swabs in SARS-CoV-2-infected individuals

Observance of a CPE after inoculation of VeroE6 cells with virus transport medium and/or a decrease of the SARS-CoV-2-RNA-PCR CT value of cell culture supernatant by 3 or more within seven days of culture will be defined as successful virus isolation (i.e., presence of infectious virus in the respective sample).

5.3.4 Frequency of COVID19-related hospitalization and medically-attended health care contacts in SARS-CoV-2-infected individuals not previously hospitalized

For SARS-CoV-2-infected individuals, information is collected on hospitalization or medically-attended health care contacts (e.g., emergency room visit) and the relationship or association with SARS-CoV-2-infection is evaluated by the investigator.

5.3.5 Time to resolution of self-assessed SARS-CoV-2-related symptoms

Date of symptom assessment for an individual subject and symptom will be obtained from the subject diary for every symptom (namely: cough, feverishness, body ache, headache, sore throat, shortness of breath, change in/loss of taste and smell) separately. Symptom evaluation scoring will take place every day on a 4-point scale (0=absent; 1=mild; 2=moderate; 3=severe), and the results entered in a subject diary. Date of resolution on the 4-point scale will be defined as the first day after drug intake where a SARS-CoV-2-related symptom is recorded as “0”. Any subsequent reoccurrence will not be considered.

For subjects with known date of symptom resolution within the first 28 days after drug intake the derivation will be as follows:

- Time to resolution [days] = Date of resolution of symptom – date of drug intake + 1

Subjects who did not experience any resolution of their existing symptom by day 29, or who have missing evaluation data, or who did not show a particular symptom at baseline will be censored according to the mechanism for censoring as described in [Table 5.3.5: 1](#) below. In particular, all subjects with no symptom at baseline will be censored at day 1, even if they later develop a symptom (after drug intake).

Table 5.3.5: 1 Censoring and Event Rules for Time to resolution of self-assessed SARS-CoV-2-related symptoms within the first 28 days after drug intake.

Rule #	Situation	Outcome (event or censored)	Date of event or censoring
1	Subject had a symptom at baseline and a resolution within the first 28 days and date of resolution is known	Event	Date of event
2	Subject had a symptom at baseline and a resolution within the first 28 days and date of resolution is unknown	Event	Imputed date of event
3	Subject had a symptom at baseline but no resolution within the first 28 days	Censored	Day 29 (28 days after first drug intake)
4	Subject had a symptom at baseline but resolution status within the first 28 days is unknown or a subject has missing assessment data	Censored	Date of last recorded consecutive follow-up entry of symptom status within the first 28 days after drug intake
5	Subject did not show a particular symptom at baseline	Censored	Day 1 (Date of drug intake)

5.3.6 Differences of viral spike gene sequences obtained before and after study drug administration and the investigation of the effect of observed mutations on viral sensitivity to DZIF-10 in neutralization assays

SARS-CoV-2 spike protein gene sequences will be determined from extracted viral RNA at baseline and after study drug administration, and analysed for the development or enrichment of non-synonymous mutations after study drug administration. Selected individual mutations, such as those within the antibody epitope or recurrent mutations, will be assessed for their impact on DZIF-10c sensitivity as determined by neutralization assays, e.g., after introducing these mutations into pseudoviruses by site-directed mutagenesis. Sensitivity results will be and reported as 50% inhibitory concentrations (IC50) and/or 100% inhibitory concentrations (IC100), if applicable, and compared to wild-type pseudovirus variants.

This further endpoint will be analysed by UKK and reported in a separate report which will be appended to the CTR.

5.3.7 The activity and frequency of SARS-CoV-2-reactive immune cells following DZIF-10c application

As described in Section 4, the analyses of this endpoint will be performed by UKK and will not be included in the CTR but might be reported elsewhere.

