### **5.2.7. Assessment of Time to Symptom Resolution**

Participants will be asked to self-record selected SARS-CoV-2 symptoms (cough, feverishness, body ache, headache, sore throat, shortness of breath, changes in/loss of taste of taste and smell) from the day of study drug administration through the day 28 visit and grade them as absent, mild, moderate, or severe using a participant diary (**Groups 2A-2D**).

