#### **5.9.7. Previous and Concomitant Medication**

Following trial drug administration, the standard of care may be provided as required by the medical condition and deemed appropriate by health care providers.

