#### Time to symptom resolution

The duration of COVID-19-related symptoms will be described based on participants's self-assessment documented on patient diaries (**Groups 2A-2D**).

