7.6.2.5 Time to resolution of self-assessed SARS-CoV-2-related symptoms

A log-rank test will be used to evaluate the effect of DZIF-10c on time to resolution of self-assessed SARS-CoV-2-related symptoms compared to Placebo over 29 days. A Cox proportional-hazards model will be used to derive the hazard ratio and 95 % CI between each of the two randomised treatment regimens that were assigned DZIF-10c and the placebo regimen (Hazard ratios <1 will favour DZIF-10c). This will be done for each symptom (cough, feverishness, body ache, headache, sore throat, shortness of breath, loss of taste or smell) separately as well as together for all symptoms. Breslow's method for handling ties will be used. Kaplan-Meier plots by treatment group will also be presented and the rates at day 29 compared.

This endpoint will be evaluated on subjects from the subject set TS.

7.6.2.6 Differences of viral spike gene sequences obtained before and after study drug administration and the investigation of the effect of observed mutations on viral sensitivity to DZIF-10c in neutralization assays

These analyses will be performed by UKK and reported in a separate report which will be appended to the CTR.

7.6.2.7 The activity and frequency of SARS-CoV-2-reactive immune cells following DZIF-10c administration

As described in Section 4, these analyses will be performed by UKK and will not be included in the CTR but might be reported elsewhere.

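### SAP 5.3.5 takes the first single diary day scored 0 as symptom resolution and ignores recurrence, so the arm comparison measures time to the first symptom-free day and may be diluted, or biased either way

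*SAP*

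**What the plan says.** SAP 5.3.5 has each symptom scored daily from 0 (absent) to 3 (severe): "Symptom evaluation scoring will take place every day on a 4-point scale". The resolution date "will be defined as the first day after drug intake where a SARS-CoV-2-related symptom is recorded as" 0. The next sentence reads: "Any subsequent reoccurrence will not be considered". No minimum number of symptom-free days is required, and the rule does not mention symptomatic medication.

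In Group 2D this date feeds a comparison of arms. SAP 7.6.2.5 states: "A log-rank test will be used to evaluate the effect of DZIF-10c on time to resolution of self-assessed SARS-CoV-2-related symptoms". It adds Cox hazard ratios with 95% confidence intervals for each DZIF-10c regimen against placebo, Kaplan-Meier plots and a comparison of day 29 rates, for each symptom and for all symptoms together. Neither that section, nor SAP 7.6.1.5 (phase I), nor the example code in SAP 9.2.2 contains a sustained-resolution analysis.

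The protocol does not define resolution. Its section 8.1.4 says: "The duration of COVID-19-related symptoms will be described based on participants's self-assessment documented on patient diaries". Section 5.2.7 has the diary kept "from the day of study drug administration through the day 28 visit", with no stop at a first 0. Under section 5.9.7, after dosing "the standard of care may be provided as required by the medical condition and deemed appropriate by health care providers".

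**The concern.** The SAP foresees that a symptom may return and discards that information. A headache scored 2, 2, 0 and then 2 on every remaining day counts as resolved on the third day, exactly like one that never comes back. The exploratory objective in Protocol 2.4 concerns the effect on symptom resolution, and Protocol 8.1.4 promises a description of duration. The first symptom-free day is neither.

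At stake is the hazard ratio. A transient 0 adds a false-event term to the daily chance of resolution in each arm. If the term is about the same in both arms, the ratio moves towards 1. If it differs, for instance because symptomatic medication is used more in one arm, the ratio can move in either direction. Both medians become shorter as well.

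**Working it through.** **Figures in the plan.** The documents state no hazard ratio, event count, power, symptom duration or recurrence rate for this endpoint, so there is nothing to reproduce. From the documents: daily scoring, a diary to the day 28 visit, 20 participants per arm, and Cox regression with Breslow ties. Durations and the rate of transient zeros below are assumptions.

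**Convention.** With resolution as the event and placebo as reference (SAP 9.2.2.2), a hazard ratio above 1 means faster resolution on DZIF-10c. SAP 7.6.2.5 states the opposite direction; that is a separate matter.

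**Model.** Let p be the daily probability of lasting resolution and q the probability of a transient 0 on a day that is still symptomatic. Under the first-0 rule the daily event probability is p + (1 − p)q. Take mean durations of 10 days on placebo (p = 1/10) and 6 days on DZIF-10c (p = 1/6). The true ratio is (1/6)/(1/10) = 1.67.

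**Equal q in both arms.**

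| q | Placebo | DZIF-10c | Ratio |
|---|---|---|---|
| 0 | 0.100 | 0.167 | 1.67 |
| 2% | 0.118 | 0.183 | 1.55 |
| 5% | 0.145 | 0.208 | 1.44 |
| 10% | 0.190 | 0.250 | 1.32 |
| 20% | 0.280 | 0.333 | 1.19 |

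At q = 10%:
- The log hazard ratio falls from ln 1.667 = 0.511 to ln 1.316 = 0.274, a loss of 0.236/0.511 = 46%.
- The share of events that are false is 0.090/0.190 = 47% on placebo and 0.083/0.250 = 33% on DZIF-10c.
- The placebo median falls from 7 days (0.9^7 = 0.48) to 4 days (0.81^4 = 0.43).

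**Unequal q, same durations, placebo q = 10%.**
- DZIF-10c q = 5%: 0.208/0.190 = 1.10.
- DZIF-10c q = 20%: 0.333/0.190 = 1.75, above the true 1.67.
- Break-even: 1/6 + (5/6)q = 1.667 × 0.190 = 0.317, so q = 18%. Above that the rule overstates the effect.

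With no true difference (simulated, median 10 days in both arms), q of 10% on placebo and 20% on DZIF-10c gives 1.57 under the SAP rule, 1.31 with two consecutive zeros and 1.02 with a 0 sustained to day 28. With 10% and 5% the SAP rule gives 0.71.

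**What other definitions recover (10 against 6 days, simulated 28-day diaries, equal q of 5, 10 and 20%).**
- Two consecutive zeros: 1.65, 1.61, 1.49.
- Sustained through day 28: 1.67, 1.66, 1.66.

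These figures assume that transient zeros are independent from day to day. If 10% of symptomatic days are transient zeros but they come in spells of two days on average, the first-0 rule gives 1.39, the two-day rule 1.50 and the sustained rule 1.66. The two-day rule then still loses about 21% of the log hazard ratio.

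**Power at 20 against 20.** Assume a true hazard ratio of 2.0, a placebo median of 10 days, equal q and a two-sided 5% log-rank test with 2,000 replicates. Power for the SAP, two-day and sustained rules is 29/53/53% at q = 5%, 18/50/57% at q = 10% and 11/33/54% at q = 20%.

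**Precision.** If all 20 per arm have the symptom and resolve, the standard error of the log hazard ratio is about √(1/20 + 1/20) = 0.32. The 95% interval around 1.32 is then about 0.71 to 2.45.

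**The case against.** The best defence is that the first 0 is a transparent, prespecified definition of an endpoint the protocol leaves undefined. The protocol names the endpoint as time to resolution, so the SAP fills a gap. A reader might infer that the SAP contradicts the protocol. It does not, although the reference to duration in Protocol 8.1.4 shows that the chosen date is narrower than what was promised. This part of the defence stands, and it is why outright replacement of the main definition is debatable.

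It also stands that little depends on this result. The endpoint is exploratory, SAP 7.5 calls any p-values nominal and SAP 4.3 limits their display, and Protocol 4.1.2 bases the antiviral assessment mainly on virological endpoints. The shift from 1.67 to 1.32 (0.236 on the log scale) is less than one standard error. Participants without the symptom at baseline are censored at day 1, so precision for a single symptom is lower still.

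Three stronger readings are tempting and not supported:
- That the rule necessarily pulls the comparison towards no effect. This needs transient zeros to be about equally common in the arms, and the documents are silent on that.
- That a single 0 ends follow-up. Only the time-to-event record ends; the diary continues to the day 28 visit.
- That the size of the distortion is known. No document says how often these symptoms come and go; the SAP only allows for recurrence. If there is none, all the definitions agree.

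**Conclusion.** The point holds in limited form. As written, SAP 5.3.5 and 7.6.2.5 compare the arms on time to the first symptom-free day, and nothing planned shows whether the answer changes for lasting resolution. With equally frequent transient zeros the hazard ratio is diluted: from 1.67 to 1.44, 1.32 or 1.19 at 5, 10 or 20%, assuming geometric durations with means of 10 and 6 days. With unequal frequency the bias can go either way, and an apparent effect can arise where there is none. The true frequency is unknown, and at zero the problem vanishes. Because the endpoint is exploratory and the arms have 20 participants each, priority is low to moderate. The reason to act is that the remedy needs no new data.

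**What to change.** Add two definitions to SAP 5.3.5 and 7.6.2.5, at least as prespecified sensitivity analyses, run with the same log-rank, Cox and Kaplan-Meier methods:

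- (a) Confirmed resolution: the first post-dose day scored 0 for which the next recorded day is also 0.
- (b) Sustained resolution: the first post-dose day from which the symptom stays 0 through the last diary entry up to day 29.

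Definition (b) matters because (a) recovers less if transient zeros cluster, and two medicated days in a row would satisfy (a).

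Label the present result *time to first symptom-free day* in text and outputs.

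Extend Table 5.3.5: 1 to say how a 0 on the last diary day without confirmation, and a 0 followed by missing entries, are censored. Rules 3 and 4 do not clearly cover either case. State whether a confirming 0 may lie beyond a gap, since Rule 4 censors at the last consecutive entry.

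State in one line that symptomatic medication is not part of the definition, and read the result beside the on-treatment concomitant therapy tables by arm that SAP 7.2.2 already plans.

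Make the change before Group 2D is unblinded; added later, the analyses should be called post hoc. Cost: SAP wording, one derivation and a small amount of programming, with no new data or burden on participants. Medians under (a) and (b) will be slightly longer and a few more participants will be censored.
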